#### **3.3.2 Inclusion Criteria**

##### DS Group

- 1) Males and females age 10 to 20 years.
- 2) Diagnosis of DS
- 3) Parental/guardian permission (informed consent) and if appropriate, child assent

##### Control Group

- 1) Males and females age 10 to 20 years
- 2) Parental/guardian permission (informed consent) and if appropriate, child assent

#### **3.3.3 Exclusion Criteria**

##### Both DS and Control Group

- 1) Major organ system illness (such as leukemia, for DS) except T2DM
- 2) Cyanotic congenital heart disease pulmonary hypertension (as described by last echo report in subjects with CHD), or congenital heart disease considered medically unstable by the study cardiologists
- 3) Pregnancy
- 4) Genetic syndrome known to affect glucose tolerance
- 5) Familial hypercholesterolemia

- 
- 6) Currently treated with medications known to affect insulin sensitivity other than diabetes agents in known T2DM subjects (e.g. oral glucocorticoids or high-dose inhaled steroids (>1000mcg/day) in the last month) or lipid profiles (statins, high dose vitamin A), or atypical antipsychotics

Subjects that do not meet all of the enrollment criteria may not be enrolled. Any violations of these criteria must be reported in accordance with IRB Policies and Procedures.

## **4 STUDY PROCEDURES**

### **4.1 Study Visit**

- Informed Consent: 30 minutes/as long as needed for parent/guardian/participant to fully comprehend the study involvement
- Fasting blood draw: 15 minutes
- Pubertal Status Exam: 5 minutes
- OGTT (Only done in subjects with BMI  $\geq$ 85thile, not known to have diabetes): 2 hours
- Vital Signs: 10 minutes
- DXA scan: 10 minutes
- Anthropometric measurements: 15 minutes
- PWV and PWA: 30 minutes
- Echocardiography: 45 minutes
- Family history of CVD, dyslipidemia, T2DM: 10 minutes
- QOL, body image, and other questionnaires: 1 hour

#### **4.1.1 Visit 1**

- Fasting Blood Sample: Will be completed by nursing staff. A total of approximately 12.5 mL (approximately 2½ teaspoons) of blood will be obtained from all participants. Subjects who do not undergo OGTT will be allowed to eat after the fasting blood sample.
- OGTT: A 2 hour OGTT will be done only in subjects with BMI  $\geq$ 85thtile, not known to have diabetes. A total of approximately 7.5 mL (1½ teaspoons) of blood will be obtained. The OGTT will be performed by nursing staff. A blood drawing IV will be placed. Baseline BG and insulin will be obtained. Subjects will ingest glucose solution (1.75 g/kg; maximum of 75 g) over 2 minutes. BG and insulin will be draw at 30, 60, 90, and 120 minutes via a blood drawing IV. For subjects refusing a blood drawing IV, BG and insulin will be drawn fasting and at 120 minutes. If a subject refuses the OGTT, only fasting labs will be obtained. Subjects who undergo OGTT will be allowed to eat after the OGTT is completed.
- Anthropometric Measurements: Performed by trained research anthropometrists, in order to assess body composition.

- 
- DXA Scan: The scan measures body composition and will be conducted and analyzed by trained staff.
  - Pubertal Status: Tanner staging of puberty will be performed by a pediatric endocrinologist team member. This exam will take place in a private exam room.
  - Pulse Wave Velocity (PWV) and Pulse Wave Analysis (PWA): The PWV and PWA will be performed by a trained technician
  - Echocardiography: Left ventricular mass will be measured by a trained sonographer and analyzed by the study cardiologist.
  - Family History of CVD, Dyslipidemia, T2DM: The study coordinator or appropriate member of the investigative team will administer a CRF to collect relevant patient medical history, family history of CVD/dyslipidemia/T2DM, sedentary and physical activity for each participant. Each question will be verbally communicated to the parent/participant, and the team member will show the questions as they are read, as appropriate.
  - Questionnaire Assessment: The following questionnaires (PedsQL, IWQOL, BES, FRS, ASAQ, CEBQ, CFQ, ABAS-II, Body Satisfaction Scales) will be administered by the study coordinator or appropriate member of the investigative team. Each questionnaire will be verbally communicated to the parent/participant, and the team member will show the questions as they are read, as appropriate. The HFI and physical activity/armband diary will be self-administered at home.
    - PedsQL - The Pediatric Quality of Life Inventory uses a modular approach to measuring health related QOL in healthy children, adolescents, and those with acute and chronic health conditions. Scales include: 1) physical functioning, 2) emotional functioning, 3) social functioning, and 4) school functioning, which yield summary scores of a total scale score, a psychosocial health summary score, and the physical health summary score.
    - IWQOL-Kids - The Impact of Weight on Quality of Life – Kids (IWQOL-Kids) © is a validated self-report measure of weight-related quality of life for youth ages 11-19. This condition-specific QOL assessment is a 27 item questionnaire that yields a total score and 4 domain scores, including physical comfort, body esteem, social life, and family relations. It has been used in children, adolescents, and in special populations.
      - IWQOL-Kids – Parent Form - The Impact of Weight on Quality of Life Kids – Parent Form (IWQOL-Parents) is a measure of the parent perception of weight-related quality of life. This condition-specific QOL assessment is a 27 item questionnaire that yields a total score and 4 domain scores, including physical comfort, body esteem, social life, and family relations.
    - BES – the Body Esteem Scale for Children is a 20-item, yes/no questionnaire designed to assess children’s attitudes and feelings about their body and appearance.
-

- 
- FRS – The Stunkard Figure Rating Scale depicts 9 male and 9 female figures, ranging in size from very thin to very overweight. It is used to assess perceptions of current and ideal body size.
  - ASAQ - The Adolescent Sedentary Activity Questionnaire is a reliable assessment of a comprehensive range of sedentary behaviors that occur in school-aged young people. In this measure, the parent will estimate the amount of time spent engaging in various sedentary activities during each day of a typical school week and weekend.
  - CEBQ – The Child Eating Behavior Questionnaire is a reliable and valid, 35 item questionnaire measuring appetite and eating style (satiety responsiveness, food enjoyment, food responsiveness, slowness in eating, food fussiness, desire to drink, emotional over-eating and emotional under-eating).
  - CFQ – The Child Feeding Questionnaire measures parental feeding practices, assessing parental beliefs, attitudes, and practices regarding child feeding. It is designed for parents of children in the age range of 2-11 years of age.
  - ABAS-II – The Adaptive Behavior Assessment System-Second Edition is widely used to evaluate individuals with intellectual and developmental disabilities measuring daily living skills (what people actually do, or can do, without the assistance of others). It assesses adaptive behavior in individuals 5-21 years of age.
  - Body Satisfaction Scales – The body satisfaction scales measure the level of satisfaction with body size, shape and weight.
  - HFI – The Home Food Inventory is a valid assessment of the home food environment. Families will be mailed the HFI prior to the study appointment and will be asked to bring the completed survey to the study appointment.
  - Physical activity/armband diary – Participants will be asked to keep a record of the times that they did not wear the physical activity armband and of their activities on the days that they wore the armband. The diary packet will be sent home with each participant, along with a postage-paid envelope to return the diary.
- 
- SenseWear® Armbands (Body Media, Inc.). Participants will be asked to wear armband accelerometers for 7 days, 24 hours per day, for 1 week with the exception of when they are bathing/showering or if participating in water activities, such as swimming. Information collected will include amount and intensity of physical activities, sedentary activities, and sleep. There are no direct benefits to participants of this assessment, but the data gleaned from these assessments will provide valuable information about the lifestyle habits of children and adolescents with Down syndrome.

## 4.2 Follow-up Phase

Dietary Intake Assessment: The twenty-four hour dietary recall will be completed by the research bionutritionists in the two to three weeks following the study visit. Three phone calls

---

(to gather information on two weekdays, one weekday) will be averaged to complete a single report.

### **4.3 Subject Completion/Withdrawal**

Subjects may withdraw from the study at any time without prejudice to their care. They may also be discontinued from the study at the discretion of the investigators for lack of adherence to study treatment or visit schedules, AEs, and/or pregnancy. The investigators may also withdraw subjects who violate the study plan, or to protect the subject for reasons of safety or for administrative reasons. It will be documented whether or not each subject completes the clinical study. If the Investigators become aware of any serious, related adverse events after the subject completes or withdraws from the study, they will be recorded in the source documents and on the CRF.

## **5 STUDY EVALUATIONS AND MEASUREMENTS**

### **5.1 Screening and Monitoring Evaluations and Measurements**

#### **5.1.1 Physical Examination**

Evaluations obtained during the study visit include Tanner staging of puberty by a pediatric endocrinologist.

#### **5.1.2 Vital Signs**

Vital signs will be recorded while the subject is sitting down by the nursing staff. BP will be measured by auscultation three times, after a five minute rest in a quiet area with the subject in a seated position; the average of the 2nd and 3rd measurements will be used.

#### **5.1.3 Laboratory Evaluations**

A fasting blood sample will be performed for the following laboratory evaluations. For those individuals undergoing the OGTT, this will be done with insertion of the intravenous (IV) line before glucose has been ingested. For individuals not requiring an OGTT, the fasting blood samples will be obtained by a routine needle stick. When necessary, commercial kits for the individual lab tests will be purchased by the investigators. Blood sampling will be performed for the following laboratory evaluations.

1. Lipid panel (TG, TC, HDL-C, LDL-C)
2. Lipoprotein subclass analysis
3. Blood glucose (BG)
4. Plasma insulin
5. High sensitivity C-reactive protein (hs-CRP)
6. Interleukin 6 (IL-6)

- 
7. Plasminogen Activator Inhibitor 1 (PAI 1)
  8. Adiponectin (total and HMW) & Leptin
  9. TSH and T4
  10. HbA1c

#### **5.1.4 Glucose Tolerance Test**

Glucose Tolerance (2-hour oral glucose tolerance test (OGTT)) will be performed by nursing staff. Subjects will be told to eat a high carbohydrate diet for 3 days before the study. Topical anesthetic ointment at the phlebotomy sites will be offered the morning of the visit. Baseline BG and insulin will be obtained. Subjects will ingest glucose solution (1.75 g/kg; maximum of 75 g) over 2 minutes. BG and insulin will be drawn at 30, 60, 90, and 120 min via a blood-drawing IV. However, the investigators realize that not all subjects will tolerate placement of the blood drawing IV, particularly given that children with Down syndrome may have developmental delays. For these subjects, BG and insulin will be drawn fasting, subjects will ingest glucose solution as described above, and a second blood draw will occur at 120 minutes. OGTT will be interpreted based on American Diabetes Association criteria: Fasting BG: <100 mg/dl = normal, 100-125mg/dl = impaired fasting glucose (IFG), ≥126 mg/dl = diabetes; 2-hour BG <140 mg/dL = normal, 140-199 mg/dL = impaired glucose tolerance (IGT), ≥200 mg/dL = diabetes.

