Study Phases	
Screening & Recruitment: Potential participants (DS group and control group) will be identified through the ambulatory electronic medical record (EMR) and primary care clinics. DS subjects may also be recruited from Endocrinology, Trisomy 21 and Cardiology clinics, DS community events, the DS Growing Up Study and local advertisements. Control subjects may also be identified through local advertisement. After potential subjects are identified, parents/guardians will be contacted to screen for eligibility. Eligible, willing subjects will be scheduled for a morning study visit after a 12 hour overnight fast.
 
Phase 1: Parental/guardian permission and child assent (if applicable) will be obtained prior to any study related procedures being performed. Subjects will undergo the following: physical exam/pubertal assessment, anthropometric measurements, vital sign assessment, fasting blood draw, 2-hour oral glucose tolerance test (OGTT), Pulse wave velocity (PWV) and Pulse Wave Analysis (PWA), echocardiography.
 
Subjects and their parent/guardian will complete the following questionnaires: The Pediatric QOL inventory (PedsQLTM), Stunkard Figure Rating Scale (FRS), Body Esteem Scale for Children (BES), Adolescent Sedentary Activity Questionnaire (ASAQ), Child Eating Behavior Questionnaire (CEBQ), Child Feeding Questionnaire (CFQ), Adaptive Behavior Assessment System-Second Edition (ABAS-II) Parent Form, the Home Food Inventory (HFI), and family history of cardiometabolic conditions. Dietary history will be obtained by three twenty-four hour dietary recall interviews will be performed over the telephone.
 
Physical activity will be assessed by accelerometry using SenseWear® Armbands. Armbands are worn for 7 consecutive days.

Efficacy	N/A in Aim 1

---

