## **6.2 Sample Size and Statistical Power**

Primary Aim: Assuming 155 evaluable children with DS and 105 evaluable children without DS for analysis and conservatively using nonparametric methods for comparison of CVD risk factors, power exceeds 0.85 to detect a between-group difference of 0.35 standard deviation (SD). For example, non-HDL-C is our primary CMR outcome measure, and 0.35 SD

---

corresponds to a difference of 7 mg/dl. A difference of 10 mg/dl is considered clinically relevant by pediatric cardiologists.

Secondary Aim: Power for the paired design can be assessed by assuming paired comparisons of residuals of a regression of BMI-Z on QOL and body image measures. Assuming that the outcomes, and thus residuals, will be continuous, power = 0.86 to detect as significant as little as 0.25 SD in differences between DS children and controls using nonparametric tests (Wilcoxon) that would be suitable for both continuous and ordered data. Thus, the sample should have substantial power to demonstrate even small differences between DS and matched controls.

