### **8.4 Recruitment Strategy**

Potential subjects will be identified using the protocol inclusion and exclusion criteria. Subjects will be recruited from multiple sources, including local primary care, Endocrinology, Cardiology and Trisomy 21 clinics, local advertisements, previous studies (if they gave permission to be contacted), and DS community events. The DS Connect recruitment registry will e-mail registry participants the IRB-approved recruitment flyer.

A study website will also be used as a source of information for potential DS and control subjects.

The Recruitment Enhancement Core (REC) will e-mail or postal mail potential control subjects using the IRB-approved REC letter for control subjects. This letter will contain opt-out language that allows study staff to contact participants via one phone call who have not opted-out 2 weeks following the letter being sent.

After the initial telephone screening, subjects that agree to participate and qualify for the study will be scheduled for an appointment. Verbal consent will be obtained by the study team prior to the screening.

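### The 3-day high-carbohydrate instruction does not say who receives it; read in context it follows the BMI cut-off for the OGTT, which can bias the BMI-Z slope for fasting outcomes and the DS-only discrimination analysis

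*Combined protocol and SAP*

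**What the plan says.** **Instruction.** Section 5.1.4 says: "Subjects will be told to eat a high carbohydrate diet for 3 days before the study". It appears nowhere else. The only preparation stated for everyone is in the Synopsis, Study Phases: "Eligible, willing subjects will be scheduled for a morning study visit after a 12 hour overnight fast".

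**Who has the OGTT.** Section 4.1.1: "A 2 hour OGTT will be done only in subjects with BMI" at or above the 85th percentile, and not in subjects with known diabetes. Table 1 and section 4.1 agree.

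**Fasting draw.** Section 5.1.3 lists lipids, lipoprotein subclasses, glucose, insulin and the inflammatory markers and adipokines as one fasting sample for all. On timing it says: "For those individuals undergoing the OGTT, this will be done with insertion of the intravenous (IV) line before glucose has been ingested". Everyone else gives the same sample by ordinary venepuncture.

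**Outcome and models.** Section 6.2: "non-HDL-C is our primary CMR outcome measure". Section 6.1 fits regressions adjusted for dietary fat intake among other confounders. Section 6.1.1 adds a DS by BMI-Z interaction. Section 6.1.3 (Aim 1d) estimates c-statistics for BMI-Z and other measures in the DS group alone.

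**Timing.** Section 4.2 places the dietary recalls within the two to three weeks after the visit. Section 8.4: "After the initial telephone screening, subjects that agree to participate and qualify for the study will be scheduled for an appointment". Table 1 schedules height and weight at Visit 1.

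**The concern.** The instruction prepares subjects for the glucose load, but the same morning's fasting sample also supplies non-HDL-C, the lipoprotein subclasses and HOMA-IR. If only OGTT subjects are told, those at or above the 85th percentile give these samples after three days of altered diet, and those below it give them on their usual diet. The primary objective is how these factors relate to BMI-Z, and a preparation switched on at a BMI cut-off acts on that relationship directly.

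No planned variable captures the run-in. The plan treats dietary fat as a confounder, but the recalls describe days after the blood draw. The Home Food Inventory is completed before the visit, but it describes the home food environment, not what the child ate. No item in Table 1 records whether the instruction was given or followed.

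ISI and the 2-hour glucose are not affected in this way, because everyone who contributes them had the OGTT.

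**Working it through.** **Plan's own figures (section 6.2).** The SD of non-HDL-C is 7 / 0.35 = 20 mg/dl. With 155 and 105 subjects, the standard error of the group difference in SD units is √(1/155 + 1/105) = 0.1264, so 0.35 / 0.1264 = 2.77. Multiplying by √0.955 (Wilcoxon efficiency) gives 2.71. Power is Φ(2.71 − 1.645) = 0.856 at one-sided 0.05, which matches the stated figure of more than 0.85, and Φ(2.71 − 1.96) = 0.772 at two-sided 0.05. The plan states neither alpha nor sidedness. That is a separate matter; only the SD of 20 is used below.

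**Inputs that are assumptions**
- d, the change in non-HDL-C (mg/dl) caused by the instruction, among those told. The documents give no value and no sign.
- BMI-Z roughly normal with SD 0.8 to 1.2.
- Half of each group at or above the cut-off. Section 6.1.1 gives 50% for DS; for controls it is inferred from BMI-Z matching.
- Residual SD 20.
- The instruction follows the cut-off exactly.

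**BMI-Z slope.** With the cut-off at the mean, regressing the indicator of being told on BMI-Z gives a slope of φ(0)/SD = 0.399/SD. The shift in the outcome slope is therefore 0.399d/SD:

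| BMI-Z SD | Shift per unit | d = 2 | d = 5 | d = 10 | Pooled slope SE, 20/(SD·√260) |
|---|---|---|---|---|---|
| 0.8 | 0.50d | 1.0 | 2.5 | 5.0 | 1.55 |
| 1.0 | 0.40d | 0.8 | 2.0 | 4.0 | 1.24 |
| 1.2 | 0.33d | 0.7 | 1.7 | 3.3 | 1.03 |

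The shift is about 0.32d standard errors whatever the SD, so it reaches one standard error at d ≈ 1.24 / 0.399 = 3.1 mg/dl. A negative d gives the same sizes with the sign reversed. If recipients were picked from a reported or earlier BMI, the switch would be blurred and the shift smaller.

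**DS contrast and interaction (BMI-Z SD 1)**
- Equal d in both groups, matched BMI-Z: both shift by about 0.
- Unequal d: the interaction shifts by about 0.40 × (d in DS − d in controls), and the DS contrast by half the difference. For 2.5 against 5, the shifts are −1.0 and −1.25. For 0 against 5, they are −2.0 and −2.5. Both standard errors are 20 × 0.1264 = 2.5.
- Matching off by 0.25 in mean BMI-Z, d = 5: the unadjusted DS contrast shifts by about 0.5 mg/dl, and by about 0 once BMI-Z is in the model.

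**Adjusting afterwards.** An indicator of being told correlates 0.399 / 0.5 = 0.80 with BMI-Z. Variance inflation is 1 / (1 − 0.798²) = 2.75, so the pooled slope SE rises from 1.24 to 1.24 × √2.75 = 2.06.

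**Aim 1d.** No c-statistic was computed, because the high/low thresholds are still to be set. BMI-Z matching gives no protection here, since the analysis uses the DS group only.

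**The case against.** The strongest objection is that the restriction to OGTT subjects is inferred. The sentence says subjects, with no BMI qualifier, and nothing in the documents says that those below the 85th percentile, or those with known diabetes, are not told. The visit is arranged after telephone screening, and height and weight come later, so telling everyone at scheduling is feasible. This stands: what is certain is that the recipients are undefined. The OGTT-only reading remains the natural one, because the sentence sits under the OGTT heading and the subjects who drink the glucose a few lines later can only be those having the test. If everyone is told, the text still needs correcting, since two sites could apply it differently without a record.

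A reader might infer that the powered DS versus control comparison of non-HDL-C is confounded. The documents do not support that. Controls are matched on BMI-Z, and with an equal diet effect neither this contrast nor the DS by BMI-Z interaction moves. Unequal adherence is plausible, since the secondary aim looks for DS-specific barriers in nutrition and feeding behaviour, but it is not documented.

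A reader might also set the slope shift against the 7 mg/dl in section 6.2. That figure is a between-group mean difference, a different estimand; the slope's own standard error is the right yardstick.

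**Conclusion.** The point holds in conditional form. The documents do not define who receives the diet instruction. On the natural reading, preparation for the fasting sample depends on BMI. The BMI-Z slope within each group then shifts by about 0.40d mg/dl per unit at BMI-Z SD 1 (0.33d to 0.50d at SD 1.2 to 0.8), against a pooled standard error of about 1.24, and the DS-only discrimination analysis is exposed by an amount not computed here. The DS contrast and the DS by BMI-Z interaction are affected only if the diet effect or adherence differs between groups; the interaction bias is then about 0.40 times the difference in d, against a standard error of about 2.5.

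The result rests on a sharp switch at the cut-off, half of each group above it, and a residual SD of 20. It cannot be turned into a predicted bias, because neither the size nor the sign of d is in the documents. It is worth correcting because the remedy is cheap and unrecorded preparation may be impossible to reconstruct later.

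**What to change.** - Reconcile the Synopsis (Study Phases) and sections 5.1.3 and 5.1.4 so that pre-visit dietary preparation is stated once, is the same for DS and control subjects, and does not depend on BMI percentile. The content of the instruction, and how subjects with known T2DM are handled, are for the sponsor to decide.
- Add one CRF item at the visit recording whether the instruction was received and followed.
- For subjects already seen, record whether the instruction was given, and repeat the lipid, HOMA-IR and Aim 1d analyses with that flag as a sensitivity analysis. State its limits: if the instruction followed OGTT eligibility, the flag has limited power to separate diet from BMI-Z; if everyone was told, it does not vary.

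The cost is a short text change, wording for the scheduling call and one CRF item. Sample size and the stated power do not change. The downside is that, if an instruction is kept, families below the cut-off also receive a short diet instruction.
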